7.6.2 Estimation of Pharmacokinetic Parameters

Noncompartmental (NCA) analysis will be performed to calculate ASP1650 pharmacokinetic parameters using Phoenix version 6.3 or higher [Certara LP, [name], US]. Descriptive statistics will be provided for the NCA-based parameters whenever applicable.

Further details on the calculation of the pharmacokinetic parameters will be provided in the SAP.

7.7 Analysis of Biomarkers

Associations between biomarkers [Section 5.7.2 Exploratory Biomarker] and clinical results (efficacy, safety, or, pharmacodynamics) may be performed on subjects in the SAF who have the necessary baseline and on-study measurements to provide interpretable results for specific parameters of interest. Biomarkers may be summarized graphically or descriptively as they relate to clinical measures, as applicable. Summary statistics may be tabulated. Additional post hoc statistical analyses may be outlined in the SAP. All analyses described in this section are based on availability of the data.

7.8 Major Protocol Deviations and Other Analyses

Major protocol deviations as defined in [Section 8.3 Major Protocol Deviations] will be summarized for all enrolled subjects by cohort, dose level and total as well as by site. A data listing will be provided by site and subject.

The major protocol deviation criteria will be uniquely identified in the summary table and listing.

7.9 Interim Analysis (and Early Discontinuation of the Clinical Study)

No formal interim analysis is planned during the Safety Lead-in phase. Safety, pharmacokinetic and other clinical data will be reviewed on an ongoing basis.

A futility analysis will be conducted 24 weeks after the first dose of the 13th subject in stage I of phase 2 of the study. The study may be stopped if less than 2 confirmed response (confirmed CR or confirmed PR by modified RECIST v1.1) are observed.

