Enrollment of 3 subjects at the target RP2D (1500 mg/m² Q2W) will begin once the 1000 mg/m² Q2W dose level has been deemed tolerable. A de-escalation dose cohort will be opened at 1250 mg/m² Q2W if 1500 mg/m² Q2W has been deemed not tolerable. Subjects enrolled in the 1000 mg/m² Q2W dose level will continue treatment at that dose level (unless they meet study treatment discontinuation criteria) and will be dose escalated to the RP2D after the RP2D is deemed tolerable.

Dose Limiting Toxicity Criteria

A DLT is defined as any of the following adverse events (AEs; graded using National Cancer Institute Common Toxicity Criteria for Adverse Events [NCI-CTCAE] version 5.0) or laboratory findings that the investigator (or sponsor) cannot clearly attribute to a cause other than study drug:

- Grade 4 neutropenia or grade ≥ 3 febrile neutropenia
- Grade 4 thrombocytopenia; or grade 3 thrombocytopenia accompanied by bleeding that requires any transfusion
- Grade 4 anemia or grade 3 anemia requiring transfusion
- Grade ≥ 3 non-hematological AE
- Aspartate aminotransferase (AST) or alanine aminotransferase (ALT) > 5 x upper limit of normal (ULN; grade ≥ 3) without liver metastases
- AST or ALT > 8 x ULN in subjects with liver metastases
- AST or ALT > 3 x ULN and total bilirubin > 2 x ULN (in subject with Gilbert syndrome: AST or ALT > 3 x ULN and **direct** bilirubin > 1.5 x ULN)
- Total bilirubin > 3 x ULN (grade ≥ 3)
- Amylase or lipase > 2 x ULN (grade ≥ 3)
- IRR that requires the infusion to be permanently discontinued

Phase 2

Once RP2D has been established as tolerable, up to 34 subjects will be enrolled in phase 2 to receive ASP1650 Q2W starting on C1D1 for up to a maximum of 12 cycles or until a study discontinuation criteria has been met, whichever occurs earlier. A Simon's 2-stage design is implemented to allow for early termination. In Simon Stage I (stage I), a total of 13 subjects, including subjects from the RP2D cohort of the Safety-Lead-in phase will be evaluated for response. If there is 1 or fewer responses among these 13 subjects, the study will be stopped early. Otherwise, an additional 21 subjects will be enrolled in Simon Stage II (stage II).

Safety Lead-in and Phase 2 Assessments

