Radiologic disease assessment will be evaluated every 6 weeks + 7 days counting from C1D1 for the first 24 weeks and then every 12 weeks \pm 7 days thereafter until the subject develops radiological disease progression per RECIST v1.1 by local investigator evaluation or starts other systemic anticancer treatment, whichever comes earlier. All measurable disease must be documented at Screening and re-assessed at each subsequent radiologic evaluation.

Imaging will include CT scans with contrast of the thorax, abdomen and pelvis. If the CT scan with contrast is medically not feasible, a CT scan without contrast or magnetic resonance imaging (MRI) may be used for imaging. Bone scans (or focal X-ray) or brain imaging may be performed if metastatic disease is suspected. The same mode of imaging should be utilized throughout the study unless medical necessity requires a change.

Blood will be drawn for the measurement of serum AFP and serum β hCG at day 1 of every cycle and during the post treatment period follow up period to align with imaging assessment (every 6 weeks + 7 days counting from C1D1 for the first 24 weeks and then every 12 weeks

± 7 days thereafter) until the subject develops radiological disease progression per RECIST v1.1 by local investigator evaluation or starts other systemic anticancer treatment.

Response assessments for the primary objective of this trial (ORR) will be made using modified RECIST v1.1. The same measurable and non-measurable lesions determined at baseline will be followed at subsequent timepoints according to RECIST v1.1. Response assessments by RECIST v1.1 and modified RECIST v1.1 will be based upon local investigator evaluation.

Safety Assessments

Safety assessments will include AEs, vital signs, ECGs, physical exams, Eastern Cooperative Oncology Group (ECOG) performance status and laboratory assessments. Severity of AEs and laboratory abnormalities will be assessed based on NCI-CTCAE.

Biomarkers and Other Sampling

An archival tumor specimen will be collected prior to first dose of study treatment. If archival tissue is unavailable or insufficient, a tumor biopsy may be performed during the screening period if the subject is an appropriate candidate for tumor biopsy.

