5.3.1.1 Imaging Assessments

Imaging assessments will be evaluated by the investigator at baseline and every 6 weeks + 7 days counting from C1D1 during the first 24 weeks and then every 12 weeks ± 7 days thereafter until the subject develops radiological disease progression per RECIST v1.1 by local investigator evaluation or starts other systemic anticancer treatment, whichever comes earlier.

All measurable disease must be documented at Screening and re-assessed at each subsequent radiologic evaluation. Imaging will include CT scans with contrast of the thorax, abdomen and pelvis. If the CT scan with contrast is medically not feasible, a CT scan without contrast or MRI may be used for imaging. Bone scans (or focal X-ray) may be performed if metastatic disease in bone is suspected. The same mode of imaging should be utilized throughout the study unless medical necessity requires a change.

Assessment of response using RECIST v1.1 [Eisenhauer et al, 2009] will be based upon local investigator evaluation. Confirmatory scans for CR or PR should be done at least 4 weeks after the date of the scan that CR or PR was first observed.

Response assessments for the primary objective of this trial (ORR) will be made using modified RECIST v1.1. The same measurable and non-measurable lesions determined at baseline will be followed by RECIST v1.1 throughout the study.

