5.3.1.2 Response Criteria Based on Modified RECIST v1.1

For subjects with measurable disease at baseline, the following criteria in [Table 4](#) will be used:

Table 4 Response Criteria Based on Modified RECIST v1.1

Serum Markers	Target Lesions	Non-Target Lesions	New Lesions	Overall Timepoint Response Assessment	
	(target lesion response)	(non-target lesion response)	(unequivocal new lesions)		
Values that fall below the ULN for the assay employed	CR	CR	No or Equivocal	CR	
	CR	Not Applicable	No or Equivocal	CR	
	Not applicable	CR	No or Equivocal	CR	
For both AFP and beta-hCG, no increase \geq 50% in 2 samples at least 1 week apart compared to nadir values, at least one of the values are above ULN	CR	CR	No or Equivocal	PR	
	CR	Not Applicable	No or Equivocal	PR	
	Not applicable	CR	No or Equivocal	PR	
For both AFP and beta-hCG, no increase \geq 50% in 2 samples at least 1 week apart compared to nadir values	CR	Non-CR/Non-PD	No or Equivocal	PR	
	CR	NE/ND	No or Equivocal	PR	
	PR	CR	} = not PD	No or Equivocal	PR
	PR	Non-CR/Non-PD		No or Equivocal	PR
	PR	NE/ND		No or Equivocal	PR
	PR	Not applicable		No or Equivocal	PR
For both AFP and beta-hCG, no increase \geq 50% in 2 samples at least 1 week apart compared to nadir values	SD	CR	} = not PD	No or Equivocal	SD
	SD	Non-CR/Non-PD		No or Equivocal	SD
	SD	NE/ND		No or Equivocal	SD
	SD	Not applicable		No or Equivocal	SD
Any	PD	Any	Any	PD	
Any	Any	PD	Any	PD	
Any	Any	Any	Yes or Unequivocal	PD	
Increase \geq 50% in serum tumor markers AFP or beta-hCG in 2 samples at least 1 week apart compared to nadir values	Any	Any	Any	PD	
NE/ND	NE/ND	Not PD	No or Equivocal	NE	

CR: complete response; ND: not done; NE: non-evaluable; PD: progressive disease; PR: partial response; SD: stable disease.

Confirmatory assessment for CR or PR should be done at least 4 weeks after the date of the CR or PR was first observed.

In subjects whose only evidence of disease is elevated serum tumor markers ($> 2 \times$ ULN AFP or $> 2 \times$ ULN β hCG) at baseline, the modified RECIST v1.1 will reduce to serum tumor marker response criteria described in Section 5.3.1.3. In subjects whose only evidence of disease is elevated serum tumor markers ($> 2 \times$ ULN AFP or $> 2 \times$ ULN β hCG) at baseline, confirmatory assessment for CR or PR is not required.

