6.10 Interim Analysis (and Early Discontinuation of the Clinical Study)

No formal interim analysis is planned during the Safety Lead-in phase. Safety, pharmacokinetic and other clinical data will be reviewed on an ongoing basis.

A futility analysis will be conducted 24 weeks after the first dose of the 13th subjects are enrolled in stage I of phase 2 of the study. The study may be stopped if we observed less than 2 confirmed response (confirmed CR or confirmed PR by modified RECIST 1.1) are observed 24 weeks after the first dose of the 13th subject.

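### The stage I futility count falls at day 168 after the 13th subject's first dose, too early to confirm a radiologic response first seen at the week-24 scan

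*Protocol*

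**What the plan says.** Protocol 7.9 fixes the date: "A futility analysis will be conducted 24 weeks after the first dose of the 13th subject in stage I of phase 2". It then gives the criterion: "The study may be stopped if less than 2 confirmed response". SAP 6.10 repeats both and words the count as responses that "are observed 24 weeks after the first dose of the 13th subject", so there the date reads as a data cut. The synopsis carries the same rule. Protocol 2.2.1 states the stopping rule without a date and more firmly: "If there is 1 or fewer responses among these 13 subjects, the study will be stopped early". Protocol 7.1 also says the trial *will* stop.

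Protocol 5.3.1.1 schedules imaging "every 6 weeks + 7 days counting from C1D1 during the first 24 weeks", and every 12 weeks (plus or minus 7 days) after that. The window in the first 24 weeks has no minus side. The same section adds: "Confirmatory scans for CR or PR should be done at least 4 weeks after the date of the scan" on which the response was first seen. For subjects whose only evidence of disease is raised serum markers, Protocol 5.3.1.2 says that "confirmatory assessment for CR or PR is not required"; SAP 5.1.1 says the same.

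The endpoint itself has no 24-week limit. SAP 5.1.1 determines best overall response once all of a subject's response data are in.

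**The concern.** The interim date and the week-24 scan start from the same clock, and the scan can only be on time or late. The analysis therefore falls on or before the last scan of the 24-week course for the 13th subject, and before anything new on that scan can be confirmed. Neither document says what to do with a CR or PR awaiting confirmation, requires the week-24 scan to be in hand, or sets a data cut-off apart from the analysis date.

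The stop boundary separates 1 response from 2. With one confirmed response and one pending, the written rule points to stopping, and stage II would not open. The stated 80% power presumes that all 13 subjects have been fully evaluated for the confirmed endpoint.

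**Working it through.** **1. Reproduce the design.** Inputs from Protocol 7.1: ORR 10% versus 25%; stop if 1 or fewer of 13 respond; reject the null if 6 or more of 34 respond.

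- P(stop | 25%) = 0.75^13 + 13 × 0.25 × 0.75^12 = 0.0238 + 0.1029 = 0.1267.
- P(reject | p) = sum over x ≥ 2 of Bin(x; 13, p) × P(at least 6 − x of 21). This gives 0.0957 at 10% and 0.8108 at 25%.

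The stated 10% and 80% are reproduced.

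**2. Calendar for the 13th subject** (elapsed days from C1D1; cut at 24 × 7 = day 168).

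| First seen at | Scan days | Earliest confirmation (+28 days) | Next scheduled scan | Against the cut |
|---|---|---|---|---|
| Week 6 | 42-49 | 70-77 | 84-91 | in time |
| Week 12 | 84-91 | 112-119 | 126-133 | in time |
| Week 18 | 126-133 | 154-161 | 168-175 | in time if scanned at 4 weeks; otherwise on or after the cut |
| Week 24 | 168-175 | 196-203 | 245-259 (week 36) | too late |

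**3. Which other subjects are exposed.** A subject first dosed d days before the 13th is at day 168 + d at the cut.

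- Response first seen at week 24, confirmed at 4 weeks: needs 168 + d ≥ 196 to 203, so d ≥ 28 to 35. Subjects dosed within about 4 to 5 weeks before the 13th are exposed.
- The same response, confirmed at the week-36 scan: needs 168 + d ≥ 245 to 259, so d ≥ 77 to 91 (11 to 13 weeks).
- Response first seen at week 18, confirmed at the week-24 scan: needs 168 + d ≥ 168 to 175. From d = 7 the whole week-24 window has closed by the cut. Only the 13th subject and anyone dosed less than a week before him are at risk.

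**4. Effect with one subject affected.** Let f be the share of his eventual confirmed responses that are still unconfirmed at the cut. The documents give no value, so f is assumed. A late response is taken to count at the final analysis if the trial continues.

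- Among the other 12: P(0 responses) = 0.75^12 = 0.0317; P(1 response) = 12 × 0.25 × 0.75^11 = 0.1267.
- P(stop | 25%) = 0.0317 + 0.1267 × [1 − 0.25(1 − f)]. The increase is 0.1267 × 0.25 × f = 0.0317f.
- Power lost = 0.0317f × P(at least 4 of 21 | 25%) = 0.0317f × 0.808 = 0.0256f.

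| f | Stop at ORR 25% | Power | Type I error |
|---|---|---|---|
| 0 (as designed) | 12.7% | 81.1% | 9.6% |
| 0.10 | 13.0% | 80.8% | 9.5% |
| 0.25 | 13.5% | 80.4% | 9.4% |
| 1 (worst case) | 15.8% | 78.5% | 9.0% |

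With one subject affected, power stays at or above 80% up to f = (0.8108 − 0.80) / 0.0256 = 0.42.

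**5. More subjects affected** (same f for each). At f = 0.10, two subjects give 13.3% stopping and 80.6% power; three give 13.6% and 80.3%. At f = 0.25, two give 14.3% and 79.8%; three give 15.2% and 79.0%. For anyone dosed a week or more before the 13th, f covers only responses first seen at week 24, so the larger value is harder to justify for him.

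**The case against.** The strongest reply is that little is lost and the sponsor can wait. The cut covers the full 12 × 14 = 168 days of treatment. Responses first seen by week 12 are confirmed in time, and a week-18 response can be confirmed from days 154 to 161 with a scan at 4 weeks, which Protocol 5.3.1.1 permits. Marker-only subjects need no confirmation under Protocol 5.3.1.2. (Protocol 5.3.1.3 sets persistence times for a confirmed marker response, which is a separate inconsistency.) Stage I includes lead-in subjects treated at the RP2D, and the amendment cites recruitment difficulty, so several first doses within five weeks of the 13th is not the natural case. All of this stands, and it keeps the effect small.

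The appeal to discretion stands only in part. Protocol 7.9 and SAP 6.10 say *may*, which lets the sponsor wait. Protocol 2.2.1 and 7.1 say *will*, and nothing guides the choice when a response is pending. Discretion also has a statistical cost. If the stop were never enforced, 6 or more of 34 alone would carry a type I error of 11.9%, so the stated 10% relies on the stop being applied.

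A reader might infer more than the documents support: that every response from week 18 onward is lost, that this holds across stage I, or that the cut ends follow-up. The calendar above rules out the first two. On the third, imaging continues until radiological progression or new systemic therapy, and best overall response uses all the data.

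**Conclusion.** The point holds in a limited form. Under the written timing, a radiologic response first seen at the week-24 scan cannot enter the futility count for the 13th subject or for others first dosed within about 4 to 5 weeks before him (up to about 13 weeks if confirmation waits for week 36). A week-18 response is at risk only for the 13th subject and anyone dosed less than a week before him, and only if confirmation waits for the week-24 scan.

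With one subject affected, wrongful stopping at ORR 25% rises by 0.3 to 0.8 percentage points under the assumed f of 0.10 to 0.25, and by 3.2 points at worst. The corresponding power losses are 0.3, 0.6 and 2.6 points, each from the unrounded values. Type I error falls slightly. The number of subjects affected and f are both assumptions.

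It would be too strong to say that the trial would be stopped wrongly or that the design fails its stated power. Under the lighter assumptions 80% power is kept, and the *may* wording leaves room to wait. The case for a change is that the decision can turn on one response, the plan is silent on a pending one, and the repair is cheap.

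**What to change.** Amend Protocol 7.9, the synopsis and SAP 6.10 together:

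- Run the futility analysis once each of the 13 stage I subjects has completed the week-24 assessment, including its +7-day window, or has progressed, died, started new anticancer therapy or left the study.
- Do not apply the stop rule while an unconfirmed CR or PR that could bring the count to 2 awaits its confirmatory assessment.
- Reconcile *may be stopped* (Protocol 7.9, SAP 6.10) with *will be stopped* (Protocol 2.2.1, 7.1).

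Thresholds and sample size stay the same, and with every stage I response settled the designed figures apply again (stop 12.7% and power 81.1% at ORR 25%, type I error 9.6%). The delay is up to 1 week in general (day 175 against 168). When a decisive response is pending it is about 5 weeks if the confirmatory scan is done at 4 weeks (203 − 168 = 35 days), and up to about 13 weeks if it waits for the week-36 scan (259 − 168 = 91 days). If all 13 subjects reach an endpoint of assessment early, the analysis can come before day 168.

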7.10 Handling of Missing Data, Outliers, Visit Windows, and Other Information

As a general principle, no imputation of missing data will be done. Exceptions are the start and stop dates of AEs and concomitant medication. The imputed dates will be used to determine whether or not an AE is treatment emergent and the medication is concomitant. Listings of the AEs and concomitant medications will present the actual partial dates; imputed dates will not be shown.

See the SAP for details of the definitions for windows to be used for analyses by visit.

8 OPERATIONAL CONSIDERATIONS

8.1 Data Collection

The investigator or site designee will enter data collected using an Electronic Data Capture system. In the interest of collecting data in the most efficient manner, the investigator or site designee should record data (including laboratory values, if applicable) in the eCRF within 5 days after the subject's visit.

The investigator or site designee is responsible to ensure that all data in the eCRFs and queries are accurate and complete and that all entries are verifiable with source documents. These documents should be appropriately maintained by the site.

The monitor should verify the data in the eCRFs with source documents and confirm that there are no inconsistencies between them.

Laboratory tests are performed at a central laboratory. Central Laboratory data will be transferred electronically to the sponsor or designee at predefined intervals during the study. The Central laboratory will provide the sponsor or designee with a complete and clean copy of the data.

All procedures conducted under the protocol must be documented.

Electronic data sources and any supporting documents should be available for review/retrieval by the sponsor/designee at any given time.

8.2 Screen Failures

For screen failures, the demographic data, reason for failing, informed consent, inclusion and exclusion criteria and AEs will be collected in the eCRF.

8.3 Major Protocol Deviations

A major protocol deviation is generally an unplanned excursion from the protocol that is not implemented or intended as a systematic change. The investigator is responsible for ensuring the study is conducted in accordance with the procedures and evaluations described in this protocol and must protect the rights, safety and welfare of subjects. The investigator should not implement any deviation from, or changes of, the protocol, unless it is necessary to eliminate an immediate hazard to study subjects.

A protocol waiver is a documented prospective approval of a request from an investigator to deviate from the protocol. Protocol waivers are strictly prohibited.

The major protocol deviation criteria are as follows:

- PD1 - Entered into the study even though they did not satisfy entry criteria,
- PD2 - Developed withdrawal criteria during the study and was not withdrawn,
- PD3 - Received wrong treatment or incorrect dose,
- PD4 - Received excluded concomitant treatment.

When a major deviation from the protocol is identified for an individual subject, the investigator or designee must ensure the sponsor is notified. The sponsor will follow-up with the investigator, as applicable, to assess the deviation and the possible impact to the safety and / or efficacy of the subject to determine subject continuation in the study.

If a major deviation impacts the safety of a subject, the investigator must contact the sponsor immediately.

The investigator will also assure that deviations meeting IRB/IEC and applicable regulatory authorities' criteria are documented and communicated appropriately. All documentation and communications to the IRB/IEC and applicable regulatory authorities will be provided to the sponsor and maintained within the trial master file.

9 END OF TRIAL

The end of the study is defined as the last visit or scheduled procedure shown in the Schedule of Assessments [Table 1] for the last study participant in the study.

Study completion is defined as the conclusion of data collection for the defined study endpoints. The study may be closed within a participating country per local regulations once the study has completed and if all subjects enrolled in the country are no longer receiving study treatment.

10 STUDY ORGANIZATION

10.1 Independent Data-Monitoring Committee (IDMC) | Data and Safety Monitoring Board (DSMB)

No IDMC or DSMB will be utilized for this study.

10.2 Other Study Organization

The DEC will be responsible for the review of safety data at specified time points in order to provide an assessment of whether reduction or escalation should occur within the next cohort and/or to determine when MTD has been reached in a given dose level. At each meeting, individual subject data will be reviewed for dose reduction or escalation decisions. Additional details regarding responsibilities and membership requirements will be included in the DEC Charter.

